### 4. Statistical Analysis Plan

Demographic, socioeconomic, medical, and ocular factors were compared across groups who did and did not receive incentives for obtaining follow-up care using unpaired t-tests for continuous data and using the Fisher's exact test for categorical data. The proportion of individuals in each group who were recommended for a follow-up comprehensive eye exam and, among those individuals, the proportion who attended that exam was compared using chi-square tests. Given the demographic differences in the study groups, the impact of incentivization was evaluated using a subset of incentivized and non-incentivized patients matched on age, sex and race. The impact of COVID-19 on follow-up attendance was estimated by correlating the rate of COVID-19 deaths in Alabama obtained from the Alabama Department of Public Health and the average number of daily hospitalizations per month with the proportion of those attending follow-up referrals during each month of the study. P-values ≤ 0.05 (two-sided) were considered statistically significant.

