### 1. Aims of the Study

Aim 1: Implement and evaluate a remote optic nerve assessment (RONA) protocol using telemedicine to identify glaucoma-associated disease in at-risk rural patients using portable multimodal structural and functional assessment of the optic nerve and retina. Also assess for diabetic retinopathy, cataract, visual acuity impairment, and refractive error.

Aim 2: Identify and evaluate remediation strategies for the barriers to patient adherence with referral and follow-up appointments by comparing the effectiveness of financial incentives along with a validated patient education program versus a validated patient education program alone.

Aim 3: Investigate the cost-effectiveness of the telemedicine program in diagnosing glaucoma using RONA versus usual in-person care from a glaucoma specialist.

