visually impaired), as well as the financial burden incurred by the individual, caregivers, and other healthcare payers. The direct medical costs of glaucoma are \$5.8 billion/year, which does not include indirect costs such as incremental nursing home placements and productivity losses. For people aged 40- 64 years, the annual medical costs of glaucoma are \$1490/person and for those aged  $\geq$  65 years, they are \$2580/person. The annual medical costs of blindness and low vision per person from all causes, including glaucoma, are \$5870 and \$10,020 for people aged 40-64 years and  $\geq$  65 years, respectively. Costeffective benefits to quality of life have been reported for early detection and treatment of eye conditions such as glaucoma. Given projected Medicare shortfalls and potential reductions in Medicaid coverage, developing high quality and efficient means to provide care for these individuals will become increasingly important.

Barriers to Eye Care. Inadequate access to eye care delays diagnosis and increases the personal and economic burdens of eye disease and visual disability. For Problems accessing eye care are the most commonly cited barrier to care by African Americans in Alabama and elsewhere. For Sport Older African Americans are less likely to receive routine comprehensive eye care, when damaging eye conditions could be detected and treated early, and less likely to adhere to prescribed glaucoma therapies, thus contributing to higher rates of eye disease. The lower rate of receiving routine eye care may be contributing to higher rates of disability from eye disease. Factors underlying lower utilization include inadequate knowledge of basic symptoms, risk factors and available treatments; reduced financial resources; limited transportation; low trust in health care providers; and high cost. Tophthalmologists rarely practice in rural areas where African Americans represent the majority of the population in Alabama. This produces a problem accessing ophthalmological care, especially subspecialist care.

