Study Design. This study had two arms. The protocol, as described below, was identical in both arms, except for the following. One arm consisted of participants not receiving any financial incentive for attending recommended follow-up care with an optometrist or ophthalmologist based on positive eye screening results. The other arm had a financial incentive, that is, participants recommended to attend a follow-up care exam with an optometrist or ophthalmologist received \$50 for attending the appointment. In the second arm, we confirmed with the eye care provider through the optometrist's or ophthalmologist's electronic medical records (EMR) whether the participant attended the follow-up appointment. We considered randomizing patients to each of the two arms. We decided not to use this approach because we were concerned that patients may talk among themselves (they live in small rural communities) about some receiving a financial incentive to attend recommended follow-up visits versus others not receiving a financial incentive. This was viewed as causing a potential conflict for patients in terms of their participating in the study and viewed as potentially unfair by patients. Thus, our approach was to first enroll half of the total number of patients in the non-financial incentive arm, and then when that was complete, to enroll the second half of the total number of patients in the financial arm. The goal was to enroll 500 patients in each arm.

**Protocol Measurements**. These are each described below. All were completed in a single visit to the FQHC. All eye and visual function measurements were performed on each eye separately. The clinical coordinators (certified ophthalmic technicians) collected all data including questionnaires.

**Demographic review.** Questionnaires obtained information on birthdate, gender, race, ethnicity, marital status, medical insurance status, transportation availability, education level, employment status, whether they received an eye examination in the past two years, reasons for not seeking an eye examination in the past two years, and contact information (address, phone number).

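### The incentive effect is estimated across sequential, non-randomised arms with adjustment for age, sex and race only; collected access and referral factors have no stated role in the estimate, and arm coincides with enrolment period

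*Combined protocol and SAP*

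**What the plan says.** Aim 2 (section 1) is a question of comparative effectiveness: "comparing the effectiveness of financial incentives along with a validated patient education program versus a validated patient education program alone". The Study Design paragraph of the Protocol explains why randomisation was rejected: patients in small communities might talk, and unequal payment might seem unfair. The plan was instead to "first enroll half of the total number of patients in the non-financial incentive arm, and then when that was complete", to enrol the incentive arm. The goal was 500 patients per arm.

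The Statistical Analysis Plan (section 4) compares attendance between arms in two ways. The first is a chi-square test among those recommended for a follow-up exam. The second is a matched analysis, in which "the impact of incentivization was evaluated using a subset of incentivized and non-incentivized patients matched on age, sex and race". The reason given for it is "Given the demographic differences in the study groups". No matching ratio, age tolerance or test for the matched data is given, and no regression, weighting or propensity method is named.

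Other covariates do appear: "Demographic, socioeconomic, medical, and ocular factors were compared across groups who did and did not receive incentives", by t-test and Fisher's exact test. Calendar time appears once, where COVID-19 deaths and hospitalisations are correlated "with the proportion of those attending follow-up referrals during each month of the study".

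The Background, under Barriers to Eye Care, lists among the factors behind low use "reduced financial resources; limited transportation; low trust in health care providers; and high cost". The Demographic review paragraph of the Protocol collects "medical insurance status, transportation availability, education level, employment status, whether they received an eye examination in the past two years". The intake form adds perceived cost of an exam, glasses and drops, and expected means of travel to follow-up. The screening form records acuity, eye pressure and fast-track urgency.

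**The concern.** Without randomisation, a difference in attendance can come from the $50, from a different mix of patients, or from a different period. The SAP deals with patient mix through three demographic variables. None of them is an access barrier of the kind that the Background itself names, and none describes why or how urgently the patient was referred. A patient sent for a 20/40 acuity and one sent urgently for high pressure may well differ in how likely they are to attend.

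Period is a separate problem. The SAP examines whether attendance moved with COVID-19 by month, but does not link this to an arm comparison that is also a comparison of two periods. As written, a significant p-value would be read as the effect of the payment, which is what Aim 2 asks about.

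**Working it through.** **No stated figure to reproduce.** The 500 per arm comes without power, referral share or attendance rates. The only relevant figures in the documents are the 500 per arm and the two-sided 0.05 level. The rates below are assumptions: 200-350 referred per arm, attendance about 50%, true incentive effect zero.

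**Step 1: bias from one unbalanced binary barrier.** Bias = (difference in barrier prevalence between arms within age, sex and race) × (difference in attendance due to the barrier).

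- Balanced: 0 × 0.25 = 0.
- 0.10 × 0.15 = 0.015, and 0.10 × 0.25 = 0.025.
- 0.20 × 0.25 = 0.050.

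The sign depends on which arm has more of the barrier.

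**Step 2: effect on the test.** With n per arm (or n pairs) at 50% attendance, SE = √(0.5/n). The false-positive rate is P(Z > 1.96 − bias/SE) + P(Z < −1.96 − bias/SE). A simulation with 2,000 runs per setting and 1:1 matching on 10-year age band, sex and race kept 155-283 pairs, about 78-81% of participants.

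| Quantity | 155 pairs | 283 pairs |
|---|---|---|
| SE (points) | 5.7 | 4.2 |
| 95% half-width (points) | 11.1 | 8.2 |
| False positives, bias 0 | 5.0% | 5.0% |
| False positives, bias 1.5 points | 5.8% | 6.5% |
| False positives, bias 2.5 points | 7.3% | 9.1% |
| False positives, bias 5 points | 14.2% | 22.1% |

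The simulation agrees. With the barrier balanced, matched bias was at most 0.1 point and false positives were 5.2-5.9%. A 10-point imbalance with a 15-25 point effect gave 1.3-2.5 points and 5.2-9.0%. A 20-point imbalance gave 3.0-5.0 points and 8.8-22.6%.

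**Step 3: what adjustment for the barrier would gain.** In the same simulation, a 17-parameter regression was fitted in all referred participants. With the barrier recorded at sensitivity 0.85 and specificity 0.90, bias fell to 0.5-1.2 points (10-point imbalance) and 1.3-2.3 points (20-point imbalance), roughly half. With poorer recording (0.70 and 0.80) only about a quarter was removed, for example from 5.0-5.2 to 3.8-3.9 points.

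**Step 4: period.** With one block of enrolment per arm, a design with intercept, arm and period has three columns but rank 2. As an illustration, take 24 months, 12 per arm: 24 month indicators plus arm make 25 columns of rank 24, so arm cannot be estimated once months are free. With a linear month trend arm can be estimated, but only through that assumption. The arm-month correlation is 0.867, so the variance is inflated by 1/(1 − 0.867²) ≈ 4.0.

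**Step 5: size of a period shift.** If average attendance differs by 5 points between the periods, with no incentive effect and the barrier balanced, both estimates are about 5 points off. In simulation, false positives were 15-22% matched and 17-27% adjusted. The adjusted rate is higher because the interval is narrower (half-width 7.4-10.2 against 8.2-11.1 points) around an estimate that is equally wrong.

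**The case against.** The sponsor gives a reasoned case for not randomising, and this point does not contest it. The matching may well cover the domain that was found to differ, since the SAP introduces it by demographic differences. Balance tables are results, and a plan need not contain them. All rates above are assumed. At a 10-point imbalance the bias is small beside a half-width of 8.2-11.1 points. All of this stands, and it makes the confounding part conditional.

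Several stronger readings are tempting, and the documents do not support them:

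- A reader might infer that the collected barriers are ignored. They are compared between arms; what is missing is a stated role in the effect estimate.
- A reader might infer that the matched estimate is known to be biased. Nothing shows whether the other factors were balanced.
- A reader might infer that every change in attendance over calendar time is misread as effect. Only a difference between the arms' period averages is.
- A reader might infer that an adjusted model solves the problem. It cannot separate arm from period, and under a period shift it gives somewhat more false positives than matching.
- A reader might infer that every useful covariate is ready to use. The visible forms show no screening-site field; the six-clinic item asks where the patient sees a primary care provider, so it does not clearly contradict the three study clinics. Perceived cost and expected travel could be influenced by arm if the $50 was disclosed at consent, which the available text does not show.

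**Conclusion.** The point holds in two parts of different strength.

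The period part follows from the design alone: arm and enrolment period coincide, and the plan does not say that this limits the Aim 2 conclusion. The size of any shift is unknown. An assumed 5-point shift would move the estimate by about 5 points.

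The patient-mix part is conditional. Bias runs from negligible, if barriers and referral reasons are balanced within age, sex and race, to about 1.5-2.5 points (10-point imbalance, 15-25 point effect) or 5 points (20-point imbalance, 25-point effect), in either direction. These figures rest on assumed rates and show scale, not the actual bias.

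This should be fixed, because much of the needed information is already collected and the change alters what the trial can conclude.

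**What to change.** 1. State in the SAP and in the Aim 2 conclusion that arm and enrolment period coincide, so the result is an association with the incentive period. Treat any COVID-19 or time-trend adjustment as a sensitivity analysis.
2. Beside the chi-square and matched results, report a covariate-adjusted risk difference (regression or propensity-weighted) with 95% CI in all referred participants. Use age, sex, race, insurance, transport availability, recent eye exam, and referral reason and urgency from the screening findings. Fix the list without reference to attendance results and collapse sparse levels. Include clinic if the screening site is recorded; otherwise use the primary-care clinic item. Put perceived cost and expected travel to follow-up in a sensitivity model unless they were asked before the incentive was disclosed.
3. Analyse the matched subset within the referred group by a method that respects the matching, and state the ratio and age tolerance.
4. Label the added analysis post hoc if outcomes have been seen. The SAP is written in the past tense and already refers to group differences, so this is likely.

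The cost is SAP wording and modest programming, provided that referral reason can be taken from the screening reports. With 17 parameters and an assumed 160-350 participants in the smaller outcome group (0.40 × 400 to 0.50 × 700), there are 160/17 = 9.4 to 350/17 = 20.6 per parameter, hence the need to collapse sparse levels. Other downsides are residual bias from imperfectly recorded barriers, a more cautious conclusion, and a narrower interval around an estimate still confounded with period. The last is why item 1 must accompany item 2.

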are mean (average, value.	
Final IOP (OS-left eye) Reading: If IOP(OS) were	
measured 3 times, use median; If measured twice, use mean value	-

03/20/2023 3:39pm

projectredcap.org

ar and a second and	
IOP greater than 30, subject requires FAST TRACK	
○ Yes ○ No	
FAST TRACK RECOMMENDATIONS	

 
○ FAST TRACK- Schedule with eye care provider within 1 Da
 
○ FAST TRACK- Schedule with eye care provider within 1 W
 
○ FAST TRACK- Schedule with an eye care provider within 2
 
	eek (IOP>35)
When is FAST TRACK subject scheduled for eye exam?	
	(Date and Time)
Where is FAST TRACK subject scheduled for eye exam? (Date and Time)	

 
UAB Department of Ophthalmology
 
UAB Lions Eye Clinic
 
[name], OD Centreville
 
Own eye care provider ( get record release)
 
	
End Time for IOP	
Warning: It has been over 30 minutes since the start time. Please check the start time and end time of IOP.	Yes No (The time period is over 30 minutes.)
Vision Screening Failure	
Did subject meet any of the below criteria (Check all that ap	ply):
☐ 20/40 or worse in either eye ☐ IOP > OR equal to 23 mmHg	
Name of referral doctor or practice	

REDCap\* 03/20/2023 3:39pm projectredcap.org

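### The COVID-19 correlation pools all study months with no arm term although the arms ran one after the other, so it can pick up part of any incentive effect

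*Combined protocol and SAP*

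**What the plan says.** The COVID-19 analysis is one sentence in the Statistical Analysis Plan: "The impact of COVID-19 on follow-up attendance was estimated by correlating the rate of COVID-19 deaths in Alabama", together with "the average number of daily hospitalizations per month", "with the proportion of those attending follow-up referrals during each month of the study". The sentence names no arm term, stratification or within-phase analysis. The section's general two-sided 0.05 threshold applies.

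The Protocol section, under Study Design, says that randomization was considered and rejected. The plan was to "first enroll half of the total number of patients in the non-financial incentive arm, and then when that was complete", to enrol the other half in the incentive arm. The goal was 500 patients per arm.

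The incentive is assessed separately. In the SAP, "the proportion who attended that exam was compared using chi-square tests", and a subset matched on age, sex and race is also used. COVID-19 appears in none of the three aims. Aim 2 concerns "comparing the effectiveness of financial incentives along with a validated patient education program versus a validated patient education program alone".

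**The concern.** The incentive is present only in the later months, and its purpose is to raise attendance. A correlation over all months compares early months with late months as well as months within a phase. If the incentive works and average COVID-19 burden was not the same in the two phases, the early-versus-late contrast mixes the two. Part of the incentive step is then read as a COVID-19 effect.

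If the incentive raises attendance, the spurious part is negative when burden was higher in the first phase and positive when it was higher in the second. The SAP calls the result an estimate of impact and tests it at 0.05. A reader could therefore take a confounded correlation as evidence that COVID-19 lowered attendance, or take a masked one as evidence that it did not.

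**Working it through.** **Inputs.** From the documents: sequential arms of 500 (Study Design); monthly correlation over all study months, no arm term, two-sided 0.05 (SAP). There is no power, attendance or COVID-19 figure to reproduce. Everything else here is assumed: 15 months per arm, 18 referrals a month, 50% attendance without incentive, and monthly burden with a within-phase coefficient of variation of 0.7. The base case has independent months and no true COVID-19 effect.

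**Step 1: direction and form.** Let A be arm (0 then 1), C monthly burden, d the incentive effect on attendance, Δ the phase difference in mean burden (second minus first), and W the within-phase variance of C. With phases of equal length and no true COVID-19 effect, the pooled slope of attendance on burden is

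d × Cov(A,C)/Var(C) = d × (Δ/4)/(W + Δ²/4).

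It is zero if d = 0 or Δ = 0, and its sign is that of d × Δ. In within-phase SD units (W = 1), |Δ| = 1 gives 0.25/1.25 = 0.20d per SD, and |Δ| = 2 gives 0.50/2 = 0.25d per SD, which is the maximum. The pick-up is therefore partial.

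**Step 2: one case by hand.** Take a 15-point effect, with burden twice as high in one phase.

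- Share of burden variance explained by arm: W = (0.7² + 1.4²)/2 = 1.225; Δ²/4 = 0.25; share = 0.25/1.475 = 0.169.
- Share of attendance variance explained by arm: sampling variance = (0.50×0.50/18 + 0.65×0.35/18)/2 = 0.01326; between phases = 0.15²/4 = 0.00563; share = 0.00563/0.01889 = 0.298.
- Expected |r| = √(0.169 × 0.298) ≈ 0.225.
- Rejection with 30 months: atanh(0.225) × √27 = 1.19, so P(Z > 1.96 − 1.19) ≈ 22%.

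Simulation gives a mean r of −0.23 with burden higher in the first phase and +0.22 when it is reversed, with rejection of about 21%.

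**Step 3: range.** False-positive rate of the correlation without arm, by formula / by simulation:

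| Incentive effect | Burden ratio 1.5 | 2 | 3 |
|---|---|---|---|
| 5 points | 6% / 6% | 7% / 7% | 9% / 9% |
| 10 points | 9% / 8% | 14% / 14% | 20% / 21% |
| 15 points | 12% / 12% | 22% / 21% | 35% / 37% |

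With no incentive effect, or equal burden, the rate is about 5%. The arm-adjusted (partial) correlation gives 4-6% throughout. Varying base attendance over 30-65% and referrals over 10-25 a month widens the unadjusted range to 5-13%, 7-29% and 8-52% at 5, 10 and 15 points.

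**Step 4: a real COVID-19 effect.** Assume a logit effect of −0.25 per SD of burden and a burden ratio of 2. If burden is higher in the incentive phase, detection without arm falls from 75% with no incentive effect to 17% at 15 points; with arm it is about 65% in both. If burden is higher in the first phase, detection without arm rises to 95% at 15 points and mean r goes from −0.45 to −0.56; the arm-adjusted r stays near −0.42.

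**Step 5: dependent months.** Assume first-order autocorrelation of 0.7 in both series, a ratio of 2 and no COVID-19 effect. The correlation without arm then rejects in about 12% of runs with no incentive effect, about 14% at 5 points and 25-27% at 15 points. The arm-adjusted one rejects in about 8-10%. The arm term removes the part due to the incentive but not the part due to serial dependence.

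**The case against.** Four points on the other side have weight.

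- **No documented magnitude.** The documents give no dates, attendance rates or COVID-19 levels by phase. On plausible inputs the result runs from nominal to a large excess, with either sign. This stands: the figures illustrate what could happen and do not measure bias in this trial.
- **Serial dependence.** With strong autocorrelation the planned test exceeds 5% even without an incentive effect, and at 5 points most of the excess comes from that source. This stands and limits what an arm term can achieve. At 15 points the omitted arm dominates.
- **Over-adjustment.** Arm and phase nearly coincide, so an arm term removes every between-phase difference, including a real fall or rise in attendance that COVID-19 caused. This stands. It is a reason to report both estimates rather than to replace one by the other.
- **Weight.** COVID-19 is outside the aims. The sequential design bears more directly on the incentive comparison, which is matched on age, sex and race but not on calendar time. That is a separate matter and does not repair the correlation.

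A reader might infer that the correlation absorbs the whole incentive effect. The documents do not support this: the pick-up is partial and needs two conditions that they do not report. Nor do they support the inference that the COVID-19 result is in fact wrong, or that this flaw alters the arm comparison, which is computed separately.

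**Conclusion.** The point holds in a conditional form. As specified, the COVID-19 correlation is open to confounding by the study's own intervention, and nothing else in the SAP guards against it; the matched subset is described only for the incentive comparison. Distortion requires both an incentive effect and a difference in mean burden between phases. If both hold, the correlation can create, hide or exaggerate a COVID-19 association.

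On the assumed inputs with independent months, the excess is slight for a small incentive effect and substantial for a large one. Those rates rest on the assumed month count, referral volume, base attendance and burden ratios, and not on trial data. Severity is low to moderate, because this is a secondary analysis and the incentive result does not depend on it.

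**What to change.** Add one or two sentences to the SAP and run a short re-analysis:

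1. Calculate monthly attendance separately by arm, using the same month definition as the planned analysis. State that definition, since the SAP does not say which date assigns a patient to a month.
2. Report the COVID-19 correlation adjusted for arm (a partial correlation, or a model with COVID-19 burden plus arm) with a 95% CI, beside the planned unadjusted correlation. Do this for deaths and for hospitalizations. Do not interpret the unadjusted figure alone as the impact of COVID-19.
3. Tabulate COVID-19 burden by arm. If the ranges barely overlap, say that the COVID-19 and incentive effects cannot be separated.
4. State that the arm-adjusted estimate describes within-phase association only, because the arm term also removes any real between-phase COVID-19 effect.
5. Label the p-values exploratory because of possible autocorrelation. A within-arm circular-shift permutation is an optional check.

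The data needed are those of the planned analysis plus arm. A scheduled-appointment date is not required.

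The cost is precision. On the assumed inputs the standard error of the COVID-19 coefficient rises by about 6%, 12% and 23% at burden ratios of 1.5, 2 and 3. If the incentive has no effect and burden differs twofold, power falls from 75% to 65%. Intervals will be wide: with 30 months, an adjusted r of −0.42 has a 95% CI of about −0.68 to −0.06.

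### The COVID-19 correlation makes no allowance for time structure, so its p-value is too small if monthly attendance drifts or steps at the change of arm

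*Combined protocol and SAP*

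**What the plan says.** The whole COVID-19 analysis is one sentence in section 4, Statistical Analysis Plan. It begins "The impact of COVID-19 on follow-up attendance was estimated by correlating the rate of COVID-19 deaths in Alabama", adds a second series, "the average number of daily hospitalizations per month", and correlates both "with the proportion of those attending follow-up referrals during each month of the study". One general rule closes the section: "P-values ≤ 0.05 (two-sided) were considered statistically significant".

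The sentence does not name the correlation coefficient, the number of months, a lag, or weights for the monthly denominators. It states no term for arm or calendar time and no handling of serial correlation. Matching on age, sex and race is stated only for the incentive comparison.

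The Study Design paragraph of the Protocol section fixes the order of the arms: "our approach was to first enroll half of the total number of patients in the non-financial incentive arm", with the incentive half enrolled afterwards. The target was 500 patients per arm.

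**The concern.** The ordinary test of a correlation counts each month as one independent observation. If both series move slowly, neighbouring months repeat much of the same information, and two unrelated series line up by chance more often than the test allows.

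That COVID-19 burden comes in waves is general knowledge rather than a figure in the documents. For attendance, the plan itself supplies a possible source of time structure. If the $50 payment works as Aim 2 hopes, the monthly attendance proportion steps up when the second arm begins. Slower drift within an arm (season, clinic capacity, referral mix) is possible but is not documented.

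At stake is one statement. A chance alignment of a COVID-19 wave with a step or drift in attendance could be reported as a significant COVID-19 effect.

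**Working it through.** **Inputs.** From the documents: two-sided 0.05, calendar month as the unit, sequential arms, 1,000 patients planned. Not in the documents, and therefore assumed: number of months, number referred, attendance rate, both autocorrelations, size of any drift or step. The plan gives no power, month count or expected correlation for this analysis, so there is no figure of its own to reproduce beyond the nominal 0.05.

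**Test.** t = r√((n − 2)/(1 − r²)), with n the number of months. All simulations below have no true COVID-19 effect and at least 20,000 replicates per setting where a count was recorded.

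**Step 1: which series matters?** Both series were first-order autoregressive (AR(1)), with autocorrelations rx and ry. False-positive rate at nominal 0.05:

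| rx / ry | n = 12 | n = 24 | n = 36 |
|---|---|---|---|
| 0 / 0 | 0.051 | 0.051 | 0.048 |
| 0.7 / 0 | 0.049 | 0.049 | 0.050 |
| 0.3 / 0.3 | 0.066 | 0.068 | 0.072 |
| 0.7 / 0.5 | 0.118 | 0.146 | 0.155 |
| 0.7 / 0.7 | 0.156 | 0.209 | 0.224 |

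One autocorrelated series is harmless; two are not. The approximate effective number of months shows why: n_eff = n(1 − rx·ry)/(1 + rx·ry). For n = 24:
- 0.7/0: 24 × 1/1 = 24, no loss.
- 0.7/0.5: 24 × 0.65/1.35 = 11.6.
- 0.7/0.7: 24 × 0.51/1.49 = 8.2.

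**Step 2: a step at the change of arm.** Binomial attendance around an assumed 60%, 24–36 months, 11–25 referred per month, COVID-19 autocorrelation 0.7:
- no step: 0.048–0.051
- 5 points: 0.061–0.071
- 10 points: 0.096–0.126
- 20 points: 0.190–0.258

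An arm term would deal with this source.

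**Step 3: drift.** 24 months × 23 referred (552) or 36 × 15 (540), mean attendance 50%, COVID-19 autocorrelation 0.7–0.85, attendance drift with autocorrelation 0.8 and SD 5–10 points:

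| Analysis | False-positive rate |
|---|---|
| Plain correlation, no drift | 0.049–0.052 |
| Plain correlation, drift | 0.068–0.149 |
| Arm removed, drift | 0.061–0.121 |
| Arm and linear time removed, drift | 0.063–0.113 |

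Repeat runs of the plain test gave 0.068–0.143 and 0.071–0.146 with drift, and up to 0.058 without. If the drift is a straight line of 10–20 points over the study (18 referred per month, COVID-19 autocorrelation 0.8), the plain test gives 0.078–0.165 and a time term restores 0.048–0.052. A linear term therefore cures a linear trend but not irregular drift.

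**Step 4: do the remedies work?**
- Circular shift of the COVID-19 series: 0.027–0.051.
- Effective-number-of-months correction: 0.041–0.078 across two sets of runs. With the autocorrelations treated as known and n = 24 it is conservative, 0.009–0.035.
- Newey-West standard errors, month-level linear model with arm and time: 0.148–0.223 (lag 3) in one set of runs and 0.08–0.21 (lags 1–3) in another. A logistic version with HAC standard errors (lag 3) gave 0.16–0.24. With no drift, HAC still gave 0.08–0.22.
- Logistic model with arm and time but no serial-correlation correction, largest drift: 0.15–0.17.

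The circular shift has a resolution limit. With n months there are n shifts, so the smallest attainable p-value is 1/n: 1/24 = 0.042, 1/36 = 0.028. Below 20 months (1/20 = 0.05) it cannot reach 0.05 at all.

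**The case against.** The strongest reply is that the harm is conditional and the analysis is minor. Both parts stand. A reader might infer that waves of COVID-19 are enough to invalidate the p-value; Steps 1 and 2 show that they are not. A reader might also infer that attendance is known to drift. No section reports that. The only time structure traceable to the documents is the possible step at the change of arm, which an arm term would absorb. What is left after an arm term is 6–12% against 5%: the low end is negligible, and the high end needs the larger assumed drift.

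A reader might further suppose that the COVID-19 result decides whether the pandemic explains the difference between arms, or that the incentive result is compromised. The documents support neither. Section 1 lists no COVID-19 aim, and section 4 does not feed the correlation into the chi-square or matched comparisons.

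It can also be said that the correlation is descriptive and the plan never asserts that months are independent. That is true of the coefficient, and if no p-value were reported the point would lapse. But the 0.05 rule covers the whole section without exception, and an ordinary correlation p-value carries the independence assumption whether or not it is stated.

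**Conclusion.** The point holds in conditional form. The plan sets a month-level correlation under a 0.05 rule with no stated allowance for serial correlation, calendar time or arm. If attendance has no time structure, the test is sound at about 5%. If attendance drifts as assumed in Step 3, the false-positive rate is about 7–15%, and about 6–12% once arm is removed. If it steps by 10 points at the change of arm, the rate is about 10–13% when arm is ignored. Because the documents give neither the study length nor any attendance or autocorrelation figure, these ranges show what could happen and do not estimate what did. The consequence is confined to the p-value and interval of an auxiliary analysis. It is worth correcting because the correction is cheap, not because a main conclusion depends on it.

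**What to change.** - Keep the month-level analysis, and state the coefficient and the number of months.
- Remove arm and calendar time before correlating.
- Take the p-value from a circular-shift permutation of the COVID-19 series. If there are fewer than 20 months, use an effective-number-of-months correction instead, with its formula named before the result is seen; its behaviour varied between versions in Step 4.
- Base any confidence interval on the effective number of months.
- Do not use HAC (Newey-West) standard errors. With 24–36 months they made the test more liberal, even without drift.
- Label the result exploratory. The section is written in the past tense, so if the correlation has already been run, say that the revised method was chosen afterwards.

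The cost is a few lines of text and a short re-analysis of data already held. Power falls somewhat and the interval widens. As an illustration, the Fisher-z standard error is 1/√(24 − 3) = 0.218 for 24 independent months and 1/√(11.6 − 3) = 0.341 with autocorrelations of 0.7 and 0.5, about 1.6 times as wide. The incentive comparison does not change.
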